Original statistical analysis plan

Version 1.0, published in July 2019.

Conservative versus Liberal fluid therapy in Septic Shock (CLASSIC) trial – statistical analysis plan

The trial protocol and statistical analysis plan were published prior to conducting the interim analyses.¹ All data analyses in the primary publication will be conducted according to this statistical analysis plan except for the changes outlined below.

Coordinating investigator

[name], Department of Intensive Care, Copenhagen University Hospital, Copenhagen, Denmark. E-mail: [contact]

Trial statistician

[name], Section of Biostatistics, University of Copenhagen, Copenhagen, Denmark. E-mail: [contact]

Trial sponsor

[name], Department of Intensive Care, Copenhagen University Hospital, Copenhagen,

Denmark. E-mail: [contact]

Protocol registration numbers

ClinicalTrials.gov identifier: NCT03668236 Ethics committee number: H-18006255 EudraCT number: 2018-000404-42 Danish Medicines Agency number: 2018020596

Trial design

The CLASSIC trial is an investigator-initiated, pragmatic, international, parallel-grouped, centrally randomised, stratified, analyst-blinded trial with adequate allocation sequence generation and allocation concealment.

Trial conduct

The protocol has been prepared according to the Standard Protocol Items: Recommendations for Interventional Trials (SPIRIT) guidelines.² The trial will adhere to this protocol, the Helsinki Declaration in its latest version,³ the international guidelines for good clinical practice (GCP)⁴, and the national laws in the participating countries.

Randomisation

Eligible patients fulfilling all inclusion criteria and no exclusion criteria are randomised 1:1 using a centralised web-based system according to a computer-generated allocation sequence list, the stratification variables and varying block sizes. The allocation sequence list and block sizes are only known by the data manager at Copenhagen Trial Unit, and remain concealed from the investigators until the last patient has completed follow-up.

Blinding

The trial intervention is not blinded for investigators, clinical staff and patients, as blinding of IV fluid restriction versus standard care is not feasible. The statistician assessing all outcomes will be masked for the allocation. The data for 90-day and 1-year mortality will be collected from electronic patient records or central national registries in most participating countries. The remaining outcomes will be provided by local investigators, who are not blinded for the intervention, by entering data from patients' files. The management committee will write the preliminary abstract with the group allocation masked; this abstract will be published as a supplement to the primary trial report.^{5,6}

Outcome measures

Primary outcome measure

The primary outcome measure is all-cause mortality at day 90 after randomisation.

Secondary outcome measures

We have 7 secondary outcome measures:

 Number of participants with one or more serious adverse events (SAEs) in the ICU defined as ischaemic events (cerebral, cardiac, intestinal or limb ischaemia) or a new episode of severe AKI (modified KDIGO3⁷)

- Number of participants with one or more serious adverse reactions (SARs) to IV crystalloids in the ICU
- Days alive at day 90 without life support (vasopressor / inotropic support, invasive mechanical ventilation or renal replacement therapy (RRT))
- Days alive and out of hospital until day 90
- All-cause mortality at 1 year after randomisation
- Health-related quality of life (HRQoL) 1 year after randomisation measured using the EuroQoL EQ-5D-5L scores ⁸
- Cognitive function 1 year after randomisation as assessed by the telephone MINI-Montreal Cognitive Assessment (MINI-MoCA) score ⁹

Detailed definitions of the outcome measures are available in the protocol.

Missing data

If less than 5% of data required for any specific analysis on primary or secondary outcomes are missing, a complete case analysis will be performed. If more than 5% are missing, and it is concluded that data are not 'missing completely at random' (MCAR criterion),^{10,11} multiple imputation using chained equations will be performed by creating 25 input datasets under the assumption that the data are 'missing at random' (MAR criterion).^{12,13}

In any multiple imputation, we will use all relevant outcomes and the stratification variables (site and metastatic or hematologic cancer), SMS-ICU¹⁴ at baseline, site of infection at baseline, comorbidities at baseline (ischemic heart disease or heart failure, chronic hypertension or chronic RRT), use of corticosteroids at baseline, mechanical ventilation at baseline, highest p-creatinine 24 hours prior to randomisation, habitual p-creatinine, p-lactate at baseline, participant weight at baseline, and volume of IV fluids given prior to randomisation. Multiple imputation will be performed separately in the two intervention groups before pooling the full dataset, and the primary result of the trial will be based on these data. The unadjusted, non-imputed analysis will also be presented. If multiple imputation is used, we will also include a best-worst worst-best case scenario to assess the potential impact of any pattern of missingness including that data are 'missing not at random' (MNAR criterion). In the 'best-worst-case' scenario it is assumed that all participants lost to followup in the experimental group e.g. have survived; and that all patients with missing outcomes in the control group have not survived. Conversely, in the 'worst-best-case' scenario, it is assumed that all participants who were lost to follow up in the experimental group have had a harmful outcome; and that all those lost to follow-up in the control group have had a beneficial outcome. When continuous outcomes are used, a 'beneficial outcome' will be defined as the group mean plus two

standard deviations (SD) of the group mean or highest possible value whichever is smallest, and a 'harmful outcome' will be defined as the group mean minus two SD of the group mean or lowest possible value whichever is highest.

General analytical principles

The analyses will be done in the intention-to-treat (ITT) population defined as all randomised participants for whom there is consent for the use of data. The conclusion of the trial will be based on the ITT analysis.

The per-protocol population is defined as the ITT population except those having one or more major protocol violations.

Statistical analyses

Primary outcome

Four analyses will be performed for the primary outcome:

Primary analysis:

1. Logistic regression analysis adjusted for the stratification variables¹⁵ (site and hematologic malignancy /metastatic cancer) in the ITT population. P-values will be two-tailed

Sensitivity analyses:

A two-tailed logistic regression analysis adjusted for the stratification variables, the SMS-ICU¹⁴ focus of infection (other foci versus urinary tract infection)^{14,16} and use of corticosteroids¹⁷
 A two-tailed logistic regression analysis in the per-protocol population adjusted for the stratification variables

4. Two-tailed logistic regression analyses in the pre-planned subgroups adjusted for the stratification variables

We will report absolute and relative risk ratios with 95% CIs for the primary analysis of the primary outcome (analysis 1) (P-value <0.05), computed using glm-models with appropriate link functions and binomial error-distribution. Further, we will report the crude event rates in each group and a Kaplan-Meier survival curve for the crude data of the primary outcome.

Secondary outcomes

Dichotomous secondary outcomes will be analysed in the same way as the primary analysis for the primary outcome, i.e.:

• SAEs

Two-tailed logistic regression adjusted for the stratification variables in the ITT population

- SARs
 Two-tailed logistic regression adjusted for the stratification variables in the ITT population
- 1-year mortality

Two-tailed logistic regression adjusted for the stratification variables in the ITT population

A Kaplan-Meier survival curve will be reported for the crude data for secondary outcome 1-year mortality.

The remaining secondary outcomes are continuous measures which we expect to be skewed (nonnormally distributed), because of inflation of specific values such as zero for 'days alive outside hospital' for all patients who die while in the ICU. The outcome measures will be analysed as follows:

- Days alive at day 90 without life support
 Generalised linear model or nonparametric test stratified for site in the ITT population
- Days alive and out of hospital at day 90
 Generalised linear model or nonparametric test stratified for site in the ITT population
- HRQoL 1-year after randomisation⁸
 Generalised linear model or nonparametric test stratified for site in the ITT population
- Cognitive function 1-year after randomisation⁹

Generalised linear model or nonparametric test stratified for site in the ITT population For the generalised linear model we will initially use Poisson distribution, alternatively negative binomial.¹⁸ If the assumptions for Poisson distribution or negative binomial distribution are not met, data will be analysed using the nonparametric Van Elteren test adjusted for site, but no other variables.¹⁹

The following secondary outcome measures are composite; SAEs, SARs, days alive at day 90 without life support. We will report each component of these outcomes in an appendix to the primary publication without P-values due to the lack of adjustment for multiple comparisons. We will report absolute and relative risk ratios with 99% CIs for dichotomous secondary outcomes. For continuous secondary outcomes we will report mean differences with 99% CIs if they are normally distributed and medians with 99% percentile-based bootstrapped CIs for non-normally distributed continuous secondary outcomes (P-value 0.01) due to the multiplicity of these. A detailed definition of the level of significance for the secondary outcomes is available in the supplement to the published statistical analysis plan. ¹

Sample size

Primary outcome

We plan to enrol 1554 (2 x 777) patients to be able to show a 15% relative risk-reduction (RRR) (7% absolute) in the restrictive group on the primary outcome from an estimated 45% 90-day mortality in the standard care group at type 1 and 2 error levels of 5% and 20% respectively, corresponding to a number needed to treat (NNT) of 14 or less. The anticipated relative risk reduction of mortality and the estimated mortality in the control group is based on data from previous RCTs and systematic reviews.^{20–24}

Trial sequential analysis of existing trials (n=8) have shown that less than 15% of the required information size of 3956 patients to detect or reject a 15% RRR in all-cause mortality with lower versus higher fluid volumes has been reached.²⁵

Secondary outcomes

We expect to have the following statistical power for the secondary outcomes based on 2 x 777 participants, a type 1 error level of 1% and a RRR of 15% in the fluid restriction group versus standard care group:

- 50% power for the number of participants with one or more SAEs (control event rate 25% ^{21,22})
- 10% power for the number of participants with one or more SARs (control event rate 5%^{21,22})

- 80% power for the mortality at 1-year (control event rate 55%^{21,22})

The estimates of the control event rates originate from data of previous septic shock trials.

We expect the following outcomes to be highly skewed (non-normally distribution): days alive without life support and out of hospital at day 90 and HRQoL and cognitive function at 1 year. As we lack sufficient knowledge on the details of the non-normal distribution no realistic power analysis can be provided. We therefore refrain from this in order to avoid creating a false impression of precision.

Pre-planned subgroup analyses

We plan to assess heterogeneity of intervention effects of the primary outcome in the following 5 subgroup analyses based on patient characteristics at baseline:

- 1. Respiratory support at randomisation (hypothesised increased effect of fluid restriction in patients receiving respiratory support)
- 2. Severe AKI defined as modified KDIGO2 or above⁷ at randomisation (hypothesised increased effect of fluid restriction in patients with severe AKI)⁷

- 3. Severe metabolic failure at randomisation defined as plasma lactate level above 4 mmol/l (hypothesised increased effect of fluid restriction in patients with severe metabolic failure)
- Participant weight at randomisation with higher weight defined as bodyweight (measured or estimated) ≥76 kg²⁰⁻²² versus lower weight as <76 kg (hypothesised increased effect of fluid restriction in patients with lower weight)
- Patients who received ≥30ml/kg body weight IV fluids in the 24 hours prior to randomisation versus patients who received a lower volume (hypothesised increased effect of fluid restriction in patients with less fluids given 24 hours prior to randomisation)

For all subgroups a P-value <0.01 in the test of interaction will be considered statistically significant. Detailed definitions of the subgroup analyses are available in the protocol.

Trial profile

At trial completion, the flow of trial participants will be reported according to the Consolidated Standards of Reporting Trials (CONSORT) statement.²⁶

Data Monitoring and Safety Committee

A Data Monitoring and Safety Committee (DMSC) has been formed, consisting of independent ICU trialists/clinicians and a biostatistician who collectively have experience in the management of ICU patients and in the conduct, monitoring and analysis of RCTs. The charter for the DMSC is available in the protocol.

Interim analyses

We will perform 3 interim analyses:

- 1. Interim analysis when 10% of patients have completed 30-days follow-up
- 2. Interim analysis when 30% of patients have completed 30-days follow-up
- 3. Interim analysis when 50% of patients have completed 90-days follow-up

For the first two interim analyses the DMSC will evaluate data on:

• Fluid volumes and protocol violations

For the third interim analysis the DMSC will evaluate data on:

• Fluid volumes, protocol violations, 90-day mortality and rates of SAEs and SARs in the ICU

The DMSC will be provided with the following masked (as group 0 and 1) data from the coordinating centre:

- Number of patients randomised
- Number of patients randomised per intervention group
- Number of patients stratified per stratification variable per intervention group
- Number of events, according to the outcomes, in the two groups

Based on evaluation of these outcomes, the DMSC will decide if they want further data from the coordinating centre. The DMSC can, at any time during the trial, request the distribution of events, including outcome measures and SARs according to intervention groups. Further, the DMSC can request unblinding of the interventions. Additionally, the DMSC will yearly be informed about SARs in the two groups of the trial.

The interim analyses will be performed by an independent statistician. The DMSC may recommend pausing or stopping the trial if a group-difference in the primary outcome measure, SARs or SUSARs are found in the interim analyses with statistical significance levels adjusted according to the LanDeMets group sequential monitoring boundaries based on O'Brien Fleming alfa-spending function.²⁷ If the recommendation is to stop the trial, the DSMC will discuss and recommend on whether the final decision to stop the trial will be made after the analysis of all participants included at the time (including participants randomized after participant number 777) and whether a moratorium shall take place (setting the trial at hold) in the further inclusion of participants during these extra analyses. If further analyses of the participants included after 777 participants is recommended, the rules for finally recommending stopping of the trial should obey the LanDeMets stopping boundary.

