7.2 Secondary outcomes

- Number of participants with one or more serious adverse events (SAEs) in the ICU defined as ischaemic events (cerebral, cardiac, intestinal or limb ischaemia) or as a new episode of severe acute kidney injury (modified KDIGO3 [41])
- Number of participants with one or more serious adverse reactions (SARs) to IV crystalloids in the ICU as defined in section 8.2
- Days alive at day 90 without life support (vasopressor / inotropic support, invasive mechanical ventilation or renal replacement therapy)
- Days alive and out of hospital at day 90
- All-cause mortality at 1-year after randomisation
- HRQoL 1-year after randomisation measured using the EuroQoL (EQ)-5D-5L and EQ-VAS scores. Participants who have died will be assigned the lowest possible scores
- Cognitive function 1-year after randomisation as assessed by the Montreal Cognitive Assessment (MoCa) score

Several of the secondary outcomes above are composite outcomes. The single components of these will also be analysed and presented in a supplement to the primary publication.

8 Safety

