10.1 Sample size and power

10.1.1 Sample size estimation

By enrolling 1554 (2 x 777) participants, we can show a 15% relative risk reduction (7% absolute) in the restrictive group from an estimated 45% 90-day mortality in the standard care group (data from our previous CLASSIC pilot, TRISS and 6S trials [2, 3, 5], systematic reviews [23, 44] and a recent large cohort study [4]) at type 1 and 2 error levels of 5% and 20% (power=80%), respectively.

The CLASSIC trial protocol Page 31/82

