10.1.2 Power estimations

We expect to have the following statistical power for the secondary outcomes based on 2 x 777 participants, a type 1 error level of 1% and a relative risk reduction of 15% in the experimental vs control group:

- 50% power for the number of participants with one or more SAEs (control event rate 25%)
- 10% power for the number of participants with one or more SARs (control event rate 5%)
- 80% power for the mortality at 1-year (control event rate 55%).

The estimates of control event rates originate in data of previous septic shock trials [2, 3]. We expect the following outcomes to be highly skewed (non-normally distribution): Days alive without life support and out of hospital at day 90 and HRQoL and cognitive function at 1-year. The power estimations for these are, therefore, somewhat uncertain why we refrain from making these estimates.

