10.2 Statistical methods

The analyses will be done in the intention-to-treat (ITT) population defined as all randomised participants for whom there is consent for the use of data. We will perform the primary analyses adjusted for the stratification variables [45] and challenge the primary result in analyses adjusted for important baseline risk factors (co-morbidities, higher SMS score, and focus of infection (other foci vs. urinary tract infection)[43, 46] and use of corticosteroids, which may reduce the time in ICU and thus the time exposed to the protocol [47]) and analyses of subgroups (Table 2) and the per-protocol population being the ITT population except those having one or more major protocol violations as defined below (Table 3). If there is more than 5% missing data for outcomes and/or covariates, we will impute the missing data using multiple imputations as described below (10.2.4).

All analyses will be 2-tailed and we will use Fisher's exact test for unadjusted comparisons of dichotomized outcomes (mortality at 90-days and 1-year, SAEs and SARs) and logistic regressions for adjusted analyses of these outcomes. The remaining secondary outcomes are continuous measures; we expect that these are highly skewed (non-normally distribution), because of inflation of specific values such as zero for days alive outside hospital for all patients who die while at the ICU. We will use statistical methods that can accommodate this type of data; the precise models will be specified in the detailed statistical plan.

Several of the secondary outcome measures are composite; we will also analyse each component of these outcomes as recommended [42]; the precise models will be specified in the detailed statistical plan.

Table 2. Heterogeneity of the intervention effects on the primary outcome will be analysed in the following subgroups based on baseline characteristics

Subgroup	Definition	Expected direction of	Statistical test
		the interaction	
Participants who are mechanically ventilated	Invasive mechanically ventilated (yes/no)	Larger effect of fluid restriction in mechanically ventilated participants	Test of interaction in the adjusted analysis described above; P- value 0.01

The CLASSIC trial protocol Page 32/82

Participants with	KDIGO (creatinine)	Larger effect of fluid	Test of interaction in
severe acute kidney	criteria of 2 or above	restriction in acute	the adjusted analysis
injury	[41] (yes/no)	kidney injury	described above; P-
			value 0.01

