- -HRQoL at 1-year (+/- 2 weeks): EQ-5D-5L and EQ-VAS scores (https://euroqol.org/) obtained by survey by mail or phone as chosen by the participant. Non-survivors will be given the worst possible score. If the participant is incapable of answering the questionnaire (e.g. due to cognitive impairment or coma) we will ask proxies to assess HRQoL for the trial participant (proxy point of view) using the questionnaire aimed for proxies. Non-survivors will be given the worst possible score. EQ-5D-5L will be converted to an index value in combination with the EQ-VAS quantitative measure (0-100 points) quantifying self-rated health
- -Cognitive function at 1-year (+/- 2 weeks): the Montreal Cognitive assessment (MoCa) MINI score (or '5-miniute protocol') using the translations of the MoCa full v. 7.1 (http://www.mocatest.org/). The score will be obtained in all survivors by interview as this was recommended to be the test of cognition in a core outcome set for patients with acute respiratory failure following a modified Delphi process involving patients, researchers and clinicians from multiple continents (http://www.improvelto.com/). Non-survivors will be given the worst possible score. The cognitive function score will be conducted before HRQoL to ensure an equal procedure and avoid that patients are disturbed or tired from the HRQoL score.

If the MoCa MINI, which is validated for phone interview [52], has not been released at the time of the first assessment (1-year after randomisation of the first patient), we will adapt the MoCa MINI from the MoCa full v. 7.1.

SARs will be defined as follows:

- -General tonic-clonic seizures: stiffening and/or jerking movements of all 4 extremities in a patient who becomes or is unconscious in the ICU after randomisation
- -Anaphylactic reactions defined as urticarial skin reaction **AND** at least one of the following observed in the ICU after randomisation
 - Worsened circulation (>20% decrease in blood pressure or >20% increase in vasopressor dose)
 - Increased airway resistance (>20% increase in the peak pressure on the ventilation)
 - Clinical stridor or bronchospasm
 - o Subsequent treatment with bronchodilators

The CLASSIC trial protocol Page 50/82

- -Central pontine myelinolysis seen on CT or MRI scan within the 90-day period after randomisation
- -Hypernatremia defined as p-Na > 159 mmol/L on any plasma sample, including point-of-care testing, done in the ICU after randomisation

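### For 1-year quality of life and cognition, the 5% complete-case rule counts deaths as observed, so about 10% of survivors can be dropped with no imputation and no missing-data sensitivity analysis

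*SAP*

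**What the plan says.** The SAP (Missing data) sets one threshold for every outcome. A complete-case analysis is done "If less than 5% of data required for any specific analysis on primary or secondary outcomes are missing". Above 5%, multiple imputation follows only if the data are judged not to be missing completely at random. The best-worst/worst-best analysis is tied to the use of multiple imputation. The threshold is pooled over arms and its denominator is not spelled out. Protocol 10.2.4 has the same 5% structure.

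For HRQoL, Protocol 7.2 states: "Participants who have died will be assigned the lowest possible scores". Protocol Appendix 2 repeats the rule under both HRQoL and cognitive function: "Non-survivors will be given the worst possible score". It also says that the cognitive score is obtained from survivors by interview. The SAP refers to the protocol for outcome definitions, so the scoring rule carries over.

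The SAP analyses both outcomes in the ITT population, meaning all randomised participants with consent for data use. The method is a generalised linear model or, failing that, the Van Elteren test.

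**The concern.** A 5% limit is meant to keep missing data too small to matter. Here about half of the analysis set is expected to be dead at 1 year and is filled in by rule, so all the non-response falls on the other half. The limit is about half as strict as it looks, for the two outcomes that depend on reaching people a year later.

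Complete-case analysis then keeps every known death and removes survivors, which raises the share of worst scores. If one arm responds less, its share rises more. The comparison can then show a group difference that reflects response alone, even when non-response is random among survivors. Because the threshold is pooled, an imbalance between arms does not trigger imputation. Below 5%, no missing-data sensitivity analysis is planned that would reveal the effect.

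**Working it through.** **Inputs from the documents**
- N = 1554, 777 per arm (Protocol 10.1.1).
- 1-year mortality 55% in controls, relative reduction 15%, alpha 1% for secondary outcomes (Protocol 10.1.2; SAP, Sample size).
- Complete-case limit of 5%, pooled (SAP, Missing data).

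**Assumptions, not in the documents**
- Survivor non-response by arm.
- Survivor score with mean 70 and SD 20 on a 0–100 scale.

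**1. The plan's N.** Two-sided 5%, 80% power, 45% vs 38%, pooled variance:

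n = [1.960·√(2·0.415·0.585) + 0.842·√(0.45·0.55 + 0.38·0.62)]² / 0.07² = 777 per arm.

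This matches the stated 2 × 777.

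**2. Survivors who may be dropped.**
- Largest number missing: 0.05 × 1554 = 77.7, so at most 77.
- Expected survivors: 777 × 0.45 + 777 × (1 − 0.55 × 0.85) = 349.65 + 413.75 = 763.4.
- Share: 77 / 763.4 = 10.1%.
- With the same mortality in both arms: 11.0% at 55%, 9.9% at 50%, 9.0% at 45%, 8.3% at 40%.

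**3. False difference with no true effect.** Let S be survival and q survivor non-response in an arm. The share of deaths in the complete-case set is (1 − S) / (1 − S·q). Take S = 0.49125 in both arms, the average of 0.45 and 0.5325; true mortality is then 50.9% in each. The false-positive rates come from simulating 777 per arm with an unstratified Wilcoxon test at 0.01, 6000 runs per row. A t-test gave nearly the same rates.

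| Survivor non-response (assumed) | Missing overall | Share of deaths analysed | False difference | False-positive rate |
|---|---|---|---|---|
| 10% vs 10% | 4.9% | 53.5% vs 53.5% | 0 | 1.0% |
| 12% vs 6% | 4.4% | 54.1% vs 52.4% | 1.6 points | 2.4% |
| 15% vs 5% | 4.9% | 54.9% vs 52.2% | 2.8 points | 5.7% |
| 16% vs 3.2% | 4.7% | 55.2% vs 51.7% | 3.5 points | 9.9% |

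Every row stays under the 5% limit. On the assumed score scale, the mean differences in the last three rows are about 1.1, 1.9 and 2.5 points.

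**4. Cross-check of the 15% vs 5% row.**
- Analysed numbers: 777 × (1 − 0.0737) = 720 and 777 × (1 − 0.0246) = 758.
- Standard error of the difference in shares: √(0.549·0.451/720 + 0.522·0.478/758) = 0.0259.
- Shift: 0.0277 / 0.0259 = 1.07 standard errors. Two-sided rejection at 2.576 is then about 6.6%, close to the simulated figure.

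**5. With a true mortality effect and equal non-response.** At 45% vs 53.25% survival and 10% non-response in both arms, the difference in survivor share is 8.21 points instead of 8.25, a negligible change.

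**The case against.** Several counter-arguments stand in part.

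- **Imbalance is assumed.** Nothing in the documents predicts unequal response. Protocol 3.3 masks the staff who assess long-term outcomes, HRQoL can be given by mail or phone, and proxies may answer for participants who cannot. This makes a large imbalance less likely. It does not exclude one: participants know their allocation, and SAP Blinding describes outcomes other than mortality as supplied by unblinded local investigators.
- **The window is narrow.** Complete-case analysis applies only when roughly 90% of survivors respond. At 85% response, 0.15 × 0.491 = 7.4% is missing overall, and the plan reaches its missingness assessment. This stands, but good follow-up is the situation the trial is aiming for.
- **The 10% is a ceiling.** Withdrawal can extend to follow-up (Protocol 4.3.1), so vital status may be unknown for some. Those cases, and missing covariates if counted, use up part of the 5%. The all-participant denominator is also inferred, although it is the natural reading for an ITT analysis.
- **The distortion could be noticed.** One-year mortality is reported separately, and participant flow follows CONSORT. An attentive reader could compare the shares of deaths, but that is no substitute for a planned analysis.

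A reader might infer that the 1-year comparisons are biased whatever happens. The documents do not support that: with equal response and equal mortality the test holds its level, and with equal response and the planned mortality effect the distortion is negligible. A reader might also put the error for the 16% vs 3.2% split at about 12%, from a two-proportion calculation on all 777 per arm. That keeps the dropped participants in the denominator and ignores the spread of survivor scores; simulation gives about 10%.

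**Conclusion.** The concern holds as a gap in the missing-data rule for two of the seven secondary outcomes. The primary outcome is not affected. What follows from the documents' own figures is that about 10% of survivors (8% to 11% over the mortality range shown) can be left out with no imputation and no sensitivity analysis, given that vital status is known and the threshold is read on the ITT set.

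The size of any resulting error rests on assumed response rates and an assumed score distribution. It is nil under equal response and mortality, small at 12% vs 6%, and material at 15% vs 5% or beyond. The simulation used an unstratified test, whereas the plan's tests are stratified for site. The change is worth making because it is cheap and closes a gap that the pooled threshold cannot detect. The documents do not show that such an imbalance is expected.

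**What to change.** For EQ-5D-5L, EQ-VAS and MoCA, state in the SAP that:

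1. The missing fraction is computed among 1-year survivors, by arm, and the 5% limit applies to that fraction. On the plan's rates, 5% of all survivors is 0.05 × 763 = 38 people instead of 77. By arm it is 17 of about 350 and 20 of about 414.
2. When the limit is exceeded, the data are treated as not missing completely at random in the ITT set, because missingness is tied to being alive. The by-arm multiple imputation already specified is then used for survivors' missing scores, with deaths fixed at the worst score, together with the best-worst/worst-best analysis.
3. Survivor response is reported by arm.

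Imputing at any level of missingness would go further than the defect requires. Under the revised rule, the largest imbalance that still escapes imputation is 5% vs 0%. The shares of deaths are then 0.50875 / (1 − 0.49125 × 0.05) = 52.2% vs 50.9%, a difference of 1.3 points.

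The cost is a few lines of SAP text and a little extra analysis work. The imputation model is by arm but not limited to survivors, so that restriction has to be added for these scores. If the 1-year analyses have already been run, the same steps can be reported as a sensitivity analysis on the existing data.
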